- Glasgow Coma Scale: A neurological scale which aims to give a reliable and objective way of recording the conscious state of a person for initial as well as subsequent assessment. A subject is assessed against the criteria of the scale, and the resulting points give a subject score between 3 (indicating deep unconsciousness) and either 15 (fully awake person).

The CT or MR imaging performed to provide a diagnosis of ICH will be used to determine hemorrhage volume using the $A \times B \times C/2$ method.

A CTA (or MRA) performed, as standard of care to rule out vascular malformations or aneurysm as well used to determine the presence of “Arterial Spot Sign” to identify an active bleed. If an active bleed is detected, additional CT/CTA/MRAs may be taken every 6 hours if per standard of care at institution and within 72 hours of ictus until hemostasis is confirmed.

An NIHSS and GCS score must be obtained prior to enrollment. The NIHSS score must be ≥ 6 and the GCS score ≥ 5 and ≤ 15 for inclusion in the study.

The Hemphill Score will be assigned based upon the clinical presentation and imaging.

A pregnancy test must be conducted for applicable subjects (female, < 50 years old and of child bearing potential).

If patient meets all eligibility criteria, they will be randomized 2:1 to either MIS or best MM alone. After a subject is randomized they will be considered enrolled. Randomization will be balanced using stratification based upon presenting condition (Hemphill Score) and hemorrhage location (primarily lobar vs. primarily deep). If randomized to surgery, MIS must be performed within 72 hours of the ictus.

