10.1 Sample Size Estimation for the Primary Outcome

The proposed study is a randomized controlled study designed to demonstrate the efficacy of MIS to improve clinical outcomes across the entire population of patients with supratentorial ICH, as well as to evaluate effect sizes within major anatomical sub-groups (e.g., deep vs. lobar hemorrhage) and cohorts (e.g. age, presenting GCS). In addition, the treatment arm will provide, for the first time, a prospective, independently adjudicated, characterization of the technical outcomes and complication rates associated with the Artemis MIS procedure.

This design provides 81% power for a cumulative odds ratio of 1.7 for the Day 180 mRS. The design's overall one-sided Type I error rate is 2.5%.

The maximum study sample size is 500 subjects and the minimum sample size is 200 subjects. The final study sample size is estimated to be low if the treatment effect is small and the study could be stopped for futility or if the treatment effect is large and the study could be stopped for expected success. The final study sample size will be high if the evidence for the treatment effect is inconclusive.

The Day 180 mRS distribution used for sample size estimation was based on control arm data from the following published studies: MISTIE⁴⁸, STICH¹³, and SICHPA⁶⁴. The distribution of mRS functional outcomes utilized in the sample size estimation is provided in Table 3.

Table 3. Distribution of mRS Functional Outcomes

mRS Distribution	0	1	2	3	4	5/6
MM	3%	10%	7%	7%	14%	59%
MIS	5%	15%	10%	9%	16%	46%

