Statistical Analysis Plan

For CLP 11899

MIND: A Prospective, Multicenter Study of Artemis a Minimally Invasive Neuro Evacuation Device, in the Removal of Intracerebral Hemorrhage

Prepared by: Penumbra Inc.

NCT number: NCT03342664

Date: January 02, 2020

1. Overview

This is a multi-center randomized controlled study designed to compare the safety and efficacy of minimally invasive hematoma evacuation with the Artemis Neuro Evacuation Device to best medical management for the treatment of intracerebral hemorrhage (ICH).

Up to 500 patients will be enrolled from up to 50 global centers (US and OUS). Each site will be limited to a maximum enrollment of up to 120 patients (~20% of total enrollment).

This Statistical Analysis Plan (SAP) will provide details to further elaborate statistical methods as outlined in the protocol and will describe analysis conventions. The SAP will be signed off prior to unblinding.

2. Sample Size

A sample size of up to 500 patients was selected for this study. Based on simulations, this trial has 81% power for a cumulative odds ratio of 1.7 with a one-sided alpha of 0.025. The minimum sample size is 200 patients (approximately 133 MIS and 67 MM).

The Day 180 mRS distribution used for sample size estimation was based on control arm data from the following published studies: MISTIE II (Hanley 2016), STICH (Mendelow 2005), and SICHPA (Teernstra 2003). The distribution of mRS functional outcomes utilized in the sample size estimation is provided in Table 1.

Table 1. Distribution of mRS functional outcomes

mRS Distribution	0	1	2	3	4	5/6
MM	3%	10%	7%	7%	14%	59%
MIS	5%	15%	10%	9%	16%	46%

3. Randomization

Randomization takes place centrally through a commercially available Interactive Web Response System (IWRS). Randomization will occur in a 2:1 ratio to either MIS or MM. The treatment allocation will be balanced by Hemphill Score (0-2, 3-4) and hemorrhage location (primarily lobar, primarily deep).

If a lack of equipoise for randomization between treatment and control occurs during trial execution, the trial randomization assignment will be revised to randomize all patients to the MIS. The minimum sample size for patients assigned to MIS treatment is 133 patients.

4. Interim Analysis

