10.1. Primary Efficacy Analysis

The primary endpoint is the Day 180 global disability assessed via the ordinal modified Rankin score (mRS).

The null hypothesis is that the cumulative odds ratio for mRS at 180 days in the MIS group compared to MM group is less than or equal to 1. The alternative hypothesis is that the cumulative odds ratio for mRS at 180 days is greater than 1. Formally, the null and alternative hypotheses to be tested are as follows:

H0: OR ≤ 1

HA: OR > 1 ,

where OR is the cumulative odds ratio for the mRS at the 180-day follow-up visit, with higher values indicating better outcomes in the MIS group.

Statistical analysis of the primary endpoint will be conducted using a logistic regression analysis of the 180-day mRS scores. The primary efficacy endpoint is met if the overall treatment effect is positive at a one-sided alpha of 0.02. The odds ratio and corresponding 95% confidence interval will be estimated from the proportional odds model. The proportional odds assumption will be assessed visually for the cumulative proportions and odds ratio estimates. The primary analysis will be unadjusted. A secondary analysis model will include the minimization variables of Hemphill Score and hemorrhage location. The mRS scores of 5 and 6 will be combined into a single group for the purposes of endpoint evaluation. Subjects deceased during study follow-up will be scored as mRS 6. As a sensitivity analysis, the mRS scores of 5 and 6 will be evaluated as separate groups.

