10.5. Efficacy Subgroup Analysis

To evaluate the impact of baseline conditions on treatment effect on functional outcome, subgroup analyses will be performed for the primary efficacy variable, 180-day ordinal mRS. Subgroup comparisons will be considered secondary analyses and will not be adjusted or used for labeling claims. The subgroups below will be used for these analyses:

- **Age** (< 65, or \geq 65)
- **Gender** (Male, or Female)
- **Race/Ethnicity**
- **Baseline Hemphill** (0-2, or 3-4)
- **Site of hemorrhage** (primarily lobar, primarily deep)
- **Geographic Location** (US, OUS)
- **Time from stroke symptom onset to randomization** (below the median, above the median)
- **Time from stroke symptom onset to sheath placement** (below the median, above the median)
- **Baseline GCS for ICH volume 20-30 cc (A x B x C/2)** (GCS \geq 9, GCS \leq 8)

The subgroup analysis will be conducted using regression with terms of treatment group and treatment-by-subgroup interaction. In addition, Hemphill Score and hemorrhage location will be included in the model. The primary statistical inference is the treatment-by-subgroup interaction, which is tested at the significance level of 0.100. These analyses will be performed on the Intent-To-Treat population. When the treatment-by-subgroup interaction is statistically significant ($p \leq 0.100$) for a specific subgroup, the treatment group differences will be evaluated within each stratum of that subgroup. Analyses stratified by geographic location will be examined for consistency with the overall trial result. A stepwise multivariate regression model with a subset of best baseline predictors for the primary endpoint of mRS will be used for the stratified analyses for consistency with the overall study result with respect to mRS. The time from stroke symptom onset to sheath placement will be evaluated for the MIS group only.

11. Safety Analysis

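### The primary mRS test ignores baseline severity recorded on every subject: a valid test, but less powerful than the collected data allow

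*SAP*

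**What the plan says.** SAP 10.1 and Protocol 10.7 specify a proportional-odds analysis of Day 180 mRS with scores 5 and 6 merged. On covariates the SAP states "The primary analysis will be unadjusted". It then adds: "A secondary analysis model will include the minimization variables of Hemphill Score and hemorrhage location". The success criterion is: "The primary efficacy endpoint is met if the overall treatment effect is positive at a one-sided alpha of 0.02". No reason is given for leaving covariates out of the deciding test.

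The severity data exist before allocation. Protocol 6.4 states "An NIHSS and GCS score must be obtained prior to enrollment" and has volume measured on the diagnostic scan. Protocol 5.1 makes age (18 to 80), volume (20 to 80 cc), NIHSS (6 or more) and GCS (5 to 15) eligibility criteria.

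Elsewhere the plan treats baseline variables as prognostic. Protocol section 10 cites an association with functional outcome for Hemphill Score and location. SAP 10.5 plans "A stepwise multivariate regression model with a subset of best baseline predictors for the primary endpoint of mRS" for stratified consistency checks. SAP section 12 plans an adjusted analysis on key baseline variables for the site analyses. None of these enters the primary test.

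On power, SAP section 2 states: "Based on simulations, this trial has 81% power for a cumulative odds ratio of 1.7 with a one-sided alpha of 0.025".

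**The concern.** When a baseline measure predicts the outcome, a proportional-odds test that ignores it has less power at the same alpha than one that includes it. Here the measures span wide ranges, are mandatory for entry and need no new assessment. The two balancing factors have only two levels each, and the primary model omits even these.

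At stake is the chance of detecting a real effect within 500 subjects, or of reaching a decision earlier. Chance imbalance is a smaller point. At the minimum size of 200 (133 MIS, 67 MM), the standard error of a standardized baseline difference is √(1/133 + 1/67) = 0.15. A covariate unrelated to the balancing factors would then differ by more than 0.2 SD in about 18% of trials. At 333:167 the standard error is 0.095 and the figure is about 3.5%.

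**Working it through.** **Inputs from the documents.** Maximum N 500; allocation 2:1; cumulative OR 1.7; MM distribution for mRS 0, 1, 2, 3, 4, 5/6 of 3, 10, 7, 7, 14, 59% (SAP Table 1); final one-sided alpha 0.02 (SAP 10.1); overall one-sided alpha 0.025 (Protocol 10.1); stated power 81%. The printed MIS row sums to 101% through rounding, so it was regenerated by applying OR 1.7 to the MM row, giving 5.0, 15.3, 9.6, 8.8, 15.6, 45.8%.

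**Input not in the documents.** Prognostic strength, taken as the share R² of variance on the latent logistic scale explained by baseline severity. It is an assumption, varied from 0.05 to 0.35.

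**Step 1: reproduce the plan's power, unadjusted, fixed sample.** Whitehead's formula, with p̄ the allocation-weighted category proportions:

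- V = N × (2/3)(1/3)/3 × (1 − Σp̄³) = 500 × 0.0741 × (1 − 0.134) = 32.08
- Noncentrality = ln(1.7) × √32.08 = 3.005
- Power at 0.02 = Φ(3.005 − 2.054) = 82.9%
- Power at 0.025 = Φ(3.005 − 1.960) = 85.2%

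A simulated unadjusted Wald test at 0.02 gave 81.8% (3,000 runs). The 81% is thus matched within 1 to 2 points at the final alpha of 0.02. Interim futility stopping could account for the remainder, but its thresholds are in the adaptive design report, which was not available.

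**Step 2: effect of adjustment, by approximation.** Start from the stated 81%: noncentrality = 0.878 + 2.054 = 2.932. Adjustment divides it by √(1 − R²), so power = Φ(2.932/√(1 − R²) − 2.054).

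| Assumed R² | Adjusted power | Gain over no adjustment |
|---|---|---|
| 0.05 | 83.0% | +2.0 |
| 0.10 | 85.0% | +4.0 |
| 0.15 | 87.0% | +6.0 |
| 0.20 | 89.0% | +8.0 |
| 0.25 | 90.8% | +9.8 |
| 0.30 | 92.7% | +11.7 |
| 0.35 | 94.3% | +13.3 |

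**Step 3: check by simulation, separating the balancing factors.** N = 500, marginal OR held at 1.7, alpha 0.02, 4,000 trials per row. Allocation was balanced on two binary factors with assumed correlations to the severity score of 0.6 and 0.3 before dichotomizing. Monte Carlo error is about 0.6 points per figure.

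| R² | Unadjusted | Two factors only | Severity score | Score minus two factors |
|---|---|---|---|---|
| 0.05 | 82.0% | 82.4% | 84.1% | +1.7 |
| 0.10 | 80.8% | 81.5% | 84.5% | +3.0 |
| 0.16 | 79.4% | 80.7% | 85.4% | +4.7 |
| 0.23 | 79.4% | 81.4% | 88.2% | +6.8 |
| 0.27 | 79.6% | 81.5% | 90.7% | +9.2 |
| 0.34 | 77.5% | 80.0% | 90.8% | +10.8 |

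The two factors alone recover 0.4 to 2.5 points; the rest needs the individual measures.

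**Step 4: risk of adjusting.** Adding the two factors and three pure-noise covariates to the severity model changed power by less than half a point. Type I error of the adjusted tests was 0.015 to 0.024 over 3,000 null runs per setting, around the nominal 0.02.

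**Step 5: which odds ratio is 1.7?** The steps above treat it as marginal. If it is the conditional value, unadjusted power is lower and the gap is as large or larger: 73.2% to 80.1% at R² 0.15, and 66.9% to 78.4% at R² 0.23 (simple 2:1 allocation).

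**The case against.** The strongest reply is that nothing here is wrong. The protocol and SAP agree, the test is pre-specified and leaves the analyst no discretion, and the plan's own power figure comes out for the unadjusted test. That stands. A reader might infer that the trial is underpowered against its target, or that its type I error is compromised; the documents support neither.

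A reader might also want one expected loss, such as 4 to 10 points. That band corresponds to R² of about 0.10 to 0.25, and nothing in the documents fixes R² there. Only the full range of roughly +2 to +13 can be defended.

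Nor can the whole gain be credited to NIHSS, age and volume. The comparison in step 2 is with no adjustment at all, so it includes whatever the Hemphill group and location carry. The documents do not list the Hemphill components, so its overlap with the individual measures is unknown.

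Three further points stand in part. The calculations assume a fixed sample and a fitted model that matches the generating one, whereas the trial has looks from 200 subjects and the real model would need several linear terms. The 133:67 imbalance applies only at the minimum size, and the secondary model and site analyses offer some supportive adjustment. Finally, SAP sections 3 and 4 allow a switch to all-MIS assignment and a comparison with MM arms pooled from public trial results. If those results are aggregate only, a model that needs individual severity values may not carry over. None of this removes the gain; it limits how precisely it can be stated and adds to the cost.

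**Conclusion.** The concern holds as lost efficiency in a valid test. Relative to no adjustment, using the recorded severity measures would raise 81% power to about 83%, 85%, 91% or 94% at assumed latent R² of 0.05, 0.10, 0.25 or 0.35. Of that gain, about 0.4 to 2.5 points could come from the two balancing factors alone, under the assumed correlations. All figures are for a fixed 500 subjects at one-sided 0.02; under the adaptive rules some of the benefit may show as earlier stopping instead of higher final power. The change is worth making because the data are already collected and the simulated penalty for weak covariates is negligible.

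**What to change.** In SAP 10.1 and Protocol 10.7, make the primary proportional-odds model include baseline NIHSS, age and hematoma volume as continuous terms, together with the Hemphill group and hemorrhage location. GCS can be left out because it overlaps NIHSS. State the functional form and which pre-randomization volume reading is used. Use the same model in the interim predictive probabilities, and re-run the design simulations to confirm that the 0.02 threshold still holds the overall 2.5%. Report the unadjusted odds ratio beside the adjusted one.

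The change should be fixed before the first interim analysis. Sign-off before unblinding, as SAP section 1 has it, is too weak a deadline when the sponsor's clinical team knows treatment assignment and interim looks begin at 200 subjects.

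The cost is revised wording, a new simulation run, and a review of whether the longitudinal imputation in SAP section 13 needs to match. The primary odds ratio also becomes conditional on severity: in the simulations a marginal 1.7 corresponded to a conditional 1.78 at R² 0.15 and 1.84 at R² 0.23. The SAP should also say which model applies if the section 4 contingency is used, since aggregate external MM data may require the unadjusted one.

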10.2. Secondary Efficacy Analysis

The secondary endpoints of Day 180 and Day 365 mRS average improvement in mRS will be analyzed using a generalized linear model. The mRS scores will be weighted as the following: 1.0 for mRS level 0; 0.91 for mRS level 1; 0.76 for mRS level 2; 0.65 for mRS level 3; 0.33 for mRS level 4; 0 for mRS level 5; and 0 for mRS level 6. Statistical analysis of the dichotomized Rankin outcome scores of 0 to 2 and 0 to 3 will be conducted with a logistic regression model. Day 365 mRS analysis will also include ordinal and dichotomous (0 to 2; 0 to 3) outcomes. Group differences will be analyzed for the following: SIS-ADL, SIS-mobility, EQ-5D-5L, length of stay, length of procedure.

10.3. Health Economics Information

The study site will complete CRFs containing healthcare utilization information (e.g. ICU days). This information may be used for analyses to compare overall healthcare costs and resource utilization between MIS and MM.

10.4. Handling of Multiplicity

There will be no adjustment on the comparison between MIS and MM on the primary effectiveness variable since the primary comparison is specified in the protocol. The following 8 secondary efficacy analyses will be adjusted using the Bonferroni correction and may be used for labeling claims:

- Stroke Impact Scale – Mobility at 180 days
- Stroke Impact Scale – ADLs at 180 days
- Stroke Impact Scale – Mobility at 365 days
- Stroke Impact Scale – ADLs at 365 days
- EQ-5D-5L at 180 days
- EQ-5D-5L at 365 days
- Length of hospital stay
- Length of ICU stay

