Interim data analysis of the primary efficacy and safety endpoints is planned after 200 subjects have been enrolled. Additional interim analyses will be conducted after every 50 subjects. The interim analyses will include imputing the 180-day mRS score for subjects who do not have 180 day scores. Based on the predictive probability that the study would be a success, the study may be stopped early for futility or enrollment may be stopped based on expected success. The specific mathematical details of the planned analyses are described in the adaptive design report.

If a lack of equipoise for randomization between treatment and control occurs during trial execution, the supplemental adaptive design report provides the details to evaluate the superiority of MIS as compared to the combined MM arms of the MIND trial and any publicly available trial results with randomized MM arms.

5. Decision Rules for Adjusting the Sample Size

The maximum study sample size is 500 subjects and the minimum sample size is 200 subjects. The final study sample size is estimated to be low if the treatment effect is small and the study could be stopped for futility or if the treatment effect is large and the study could be stopped for expected success. The final study sample size will be high if the evidence for the treatment effect is inconclusive. The specific decision rules for sample size adjustments are described in the adaptive design report.

6. Analysis Populations

All primary and secondary effectiveness endpoints will be performed for both the intent-to-treat (ITT) population and per-protocol (PP) population.

- 6.1. Target Population: The target population is patients 18-80 years of age who have a diagnosis of spontaneous, non-traumatic, intracerebral hemorrhage (ICH) ranging in volume between and including 20 and 80 cc, with an associated significant neurological deficit (NIHSS > 6) who do not require emergent open surgical decompression related to uncontrolled intracranial pressure or mass effect.
- 6.2. Intent to Treat Sample: As the primary analysis, all efficacy and safety outcome measures will be analyzed under the intent-to-treat (ITT) principle. Under this principle, the evaluable sample includes all subjects who are randomized. Each subject will be analyzed according to the treatment group to which they were randomly assigned at the time of randomization. This population is the primary population for all efficacy parameters.

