- 6.3. Per Protocol Sample: In addition to the defined ITT analysis sample, a per-protocol (PP) sample is defined as a subset of the ITT sample. The per-protocol sample will include all randomized subjects that do not have significant protocol deviations (e.g. eligibility violation, crossover).
- 6.4. Safety Analysis (As Treated) Sample: In the case of cross-overs, a safety sample that is the same as the ITT sample will be examined in which subjects will be analyzed according to the actual treatment received. Subjects who receive Artemis device-based therapy are included in the MIS arm and subjects who receive only medical therapy are included in the MM arm.

6.5. The following additional population definitions apply to this study:

- 6.5.1.Screened: All patients considered for participation in the study, whether or not they sign an informed consent.
- 6.5.2.Screen Failure: All patients considered for participation in the study, who failed to meet inclusion or met exclusion criteria. Patients can be screen failed based on general or imaging criteria. These patients may or may not have signed an informed consent.
- 6.5.3.Enrolled (Randomized): All subjects who have been randomized based on the result of the baseline imaging and other inclusion/exclusion criteria. Informed consent must be obtained prior to randomization.
- 6.5.4.Completed: All subjects who were enrolled (randomized) and completed the study follow-up or were known to have died prior to the follow-up timepoint. The completed subject metric will be provided for Day 180 and Day 365 follow-up.
- 6.5.5.Early Termination: Subjects who were enrolled (randomized) but did not complete follow-up and were not known to have died. The early termination subject metric will be provided for Day 180 and Day 365 follow-up.

7. Statistical Methods

Summary tables (descriptive statistics and/or frequency tables) will be provided for all baseline variables, efficacy variables, and safety variables, as appropriate. Continuous variables will be summarized with descriptive statistics (n, mean, standard deviation, range, and median).

Frequency counts and percentage of subjects within each category will be provided for categorical data. Based on the variable distribution, parametric or non-parametric tests will be used for comparisons between groups.

8. Baseline Characteristics

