11.3. Handling of Multiplicity

There will be no adjustment for multiple comparisons between MIS and MM on the primary safety variable since the primary comparison is specified in the protocol; all other safety comparisons will be considered secondary analyses and will not be adjusted or used in labeling claims.

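### SAP 10.4 lets eight Bonferroni-adjusted secondary endpoints support labeling claims without requiring that the primary be met and without a family alpha or sidedness; their handling of deaths and missing scores is also left open

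*SAP*

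**What the plan says.** SAP 10.4 leaves the primary comparison unadjusted and then states: "The following 8 secondary efficacy analyses will be adjusted using the Bonferroni correction and may be used for labeling claims". The eight are the Stroke Impact Scale (SIS) mobility and ADL domains and EQ-5D-5L, each at Days 180 and 365, plus length of hospital stay and of ICU stay. The section says no more about them.

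Elsewhere the SAP restricts claims explicitly. On subgroups (SAP 10.5): "Subgroup comparisons will be considered secondary analyses and will not be adjusted or used for labeling claims". Safety comparisons other than the primary one (SAP 11.3) "will not be adjusted or used in labeling claims".

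The only alphas given for an efficacy comparison belong to the primary. It is met if the effect is "positive at a one-sided alpha of 0.02" (SAP 10.1), and Protocol 10.1 says the design's "overall one-sided Type I error rate is 2.5" per cent. The 0.10 and 0.15 levels in SAP 10.5 and SAP 12 are for interaction tests.

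For the analysis itself, SAP 10.2 says only that group differences in SIS, EQ-5D-5L and stay will be analyzed, and SAP 7 adds: "Based on the variable distribution, parametric or non-parametric tests will be used for comparisons between groups". Death has a value for mRS (scored 6, SAP 10.1) and for the weighted mRS (weight 0, SAP 10.2). Imputation in SAP 13 covers the 180-day mRS for the primary endpoint.

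**The concern.** These eight are the only secondary endpoints that the SAP names as possible support for labeling. Bonferroni controls error within the eight once an alpha is fixed. It does not control error across the primary and the eight together, and without an alpha and a sidedness it has no computable threshold.

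Two things follow. A trial that fails on disability could still yield a labeling claim on quality of life or length of stay. And the bar for that claim could be settled late, when it should be fixed in advance.

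The treatment of deaths raises a smaller, separate question. Mortality is substantial in this disease, and SIS, EQ-5D-5L and stay have no obvious value for a patient who has died. Neither primary endpoint is affected by any of this.

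**Working it through.** **The plan's own figure.** The documents give no figure for the secondary family, so I start with the stated 81% power for the primary. Inputs from SAP 2 and 3: N = 500, allocation 2:1 (k = 2), the MM row of Table 1, odds ratio 1.7. For the proportional odds model, V = N·k/[3(k+1)²]·(1 − Σp̄³), where p̄ is the pooled distribution. Shifting MM by 1.7 gives Σp̄³ = 0.134, so V = (1000/27) × 0.866 = 32.1. The mean z is ln(1.7) × √32.1 = 3.00. Power is Φ(3.00 − 2.054) = 82.9% at one-sided 0.02, and 85.2% at one-sided 0.025. The stated 81% comes from simulating an adaptive design that can stop for futility, so a value slightly below 82.9% is plausible.

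**What threshold does Bonferroni imply?**
- One-sided 0.02/8 = 0.0025: z = 2.807.
- One-sided 0.025/8 = 0.003125 (the same bar for benefit as two-sided 0.05/8): z = 2.734.
- One-sided 0.05/8 = 0.00625: z = 2.498.

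The text does not choose among these.

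**False claims when there is no effect on anything.** Assume one-sided 0.025 for the family and 0.02 or 0.025 for the primary. With independent tests the chance of any false claim is 1 − 0.98 × (1 − 0.003125)⁸ = 1 − 0.98 × 0.97527 = 0.044, or 0.049 with 0.975 in place of 0.98. The chance of a secondary claim after a failed primary is 0.98 × (1 − 0.97527) = 2.4%.

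With a common correlation ρ among all nine tests, let F(c) = Φ((c − √ρ·g)/√(1−ρ)). The chance of any false claim is 1 − ∫F(c₁)·F(c₂)⁸·φ(g)dg, where c₁ and c₂ are the primary and secondary critical values.

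| Correlation | Any false claim | Claim after failed primary |
|---|---|---|
| 0 | 0.044–0.049 | 2.4% |
| 0.3 | 0.040–0.045 | 2.0% |
| 0.6 | 0.032–0.037 | 1.2% |
| 0.9 | 0.022–0.026 | 0.1–0.2% |

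For independent tests, a family alpha of one-sided 0.02 gives 0.039–0.044, and one-sided 0.05 gives 0.068–0.073. If the eight are tested only after the primary is met, the chance under this global null is the primary's own 0.02–0.025.

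**Why that condition alone is not enough.** Suppose the primary effect is real (mean z = 3, tested at 0.02), the eight have no effect, and the family is tested at one-sided 0.05 after the primary succeeds. With independent tests a false secondary claim occurs in 0.828 × 0.0489 = 4.1% of trials. The same integration, with the primary's mean shifted by 3, gives 4.2% at correlation 0.3 and 3.3% at 0.6. The alpha must therefore be stated as well.

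**What the condition costs.** Assume odds ratio 1.7, N = 500, secondary mean z values evenly spread from 2 to 3, and Holm at one-sided 0.02. By simulation, mean true claims out of eight fall from about 3.70 to 3.33 (correlation 0.3) or from 3.73 to 3.58 (0.6). Unconditional Bonferroni at the same alpha gives about 3.08 at correlation 0.3.

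**Deaths, as a sensitivity only.** Take 9% against 15% mortality, the 30-day figures that Protocol 1.3.2.1 cites from another trial. Assume identical survivors in both arms, with mean EQ-5D-5L 0.60, stay 14 days, and 5 days for patients who die in hospital.
- EQ-5D-5L: the survivors-only difference is 0. With death scored 0 it is 0.60 × (0.91 − 0.85) = 0.036 in favour of the lower-mortality arm.
- Stay: the survivors-only difference is 0. Counting observed days gives 14 × 0.91 + 5 × 0.09 = 13.19 against 14 × 0.85 + 5 × 0.15 = 12.65, so the lower-mortality arm looks 0.54 days worse.

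The open rule can therefore push a result in either direction.

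**The case against.** The strongest reply is that SAP 10.4 is silent, not permissive. A reader might infer from the explicit bars in SAP 10.5 and 11.3 that claims are allowed whether or not the primary succeeds. The text does not say that, and the contrast supports only an inference. What stands is that no condition is stated anywhere in the two documents. The adaptive design report is not available here, but the documents cite it for interim analyses, sample-size rules and the loss-of-equipoise supplement, not for secondary multiplicity.

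A reader might also infer that the 2.5% Type I error rate is exceeded. It is not: Protocol 10.1 states that rate for the primary design and promises nothing across the secondaries. The excess is also modest. Independence is implausible for two SIS domains and EQ-5D-5L at two visits plus two overlapping stay measures, and at high correlation the excess nearly vanishes. Bonferroni itself is valid; Holm is an improvement, not the correction of an error.

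On deaths, a reader might infer that the plan analyzes survivors only. That is a likely default, not a stated rule. SAP 6.2 says "all efficacy and safety outcome measures will be analyzed under the intent-to-treat (ITT) principle", and SAP 6.5.4 counts as completed those who "completed the study follow-up or were known to have died prior to the follow-up timepoint"; neither says what value a dead patient receives. Nor should a stay result that favours the lower-mortality arm be called false when death counts as a bad outcome and mortality truly differs: on that estimand it is true. The illustrations rest on assumed values and do not size an error in this trial.

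**Conclusion.** The point holds as a gap in specification that should be closed. SAP 10.4 names eight endpoints for possible labeling claims without requiring success on the primary and without an alpha or sidedness, and no other section supplies them. If nothing works, a claim after a failed primary would arise in about 1.2% to 2.4% of trials at correlations from 0.6 down to 0, and in 0.1% to 0.2% at 0.9. These figures assume a family alpha of one-sided 0.025 and equal correlation among the nine tests; neither is in the documents. The missing rules for deaths and missing scores are a secondary point: a real omission whose effect can go either way and cannot be sized from the documents.

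**What to change.** In SAP 10.4:
- (a) Test the eight for labeling claims only if the primary efficacy endpoint is met.
- (b) State the family alpha and sidedness, for example one-sided 0.02, the primary's own level.
- (c) Replace Bonferroni with Holm, which has the same error control and never claims less.

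In SAP 10.2, before unblinding, give one rule for deaths and one for missing scores per endpoint. For the scales, a patient dead by the visit could score 0 on EQ-5D-5L and the worst value on SIS, in line with the zero weight the SAP already gives mRS 6, with survivors-only summaries alongside. For stay, state the estimand and word any claim to match it. If death counts against an arm, the claim is about being alive and discharged. Imputing survivors' missing scores by arm from earlier visits is one option, not a requirement.

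The cost is wording; no new data are needed. The real downside of (a) is that no labeling claim is possible if the primary fails. Under the assumed effects it removes about 0.37 true claims on average (3.70 − 3.33) at correlation 0.3, or 0.15 (3.73 − 3.58) at 0.6. Holm's gain should not be used to hide that loss, since Holm is available without the condition. Scoring death on the scales mixes survival with function, which is why the survivors-only summaries should stay.
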